19.8 Correlative Data Analysis

Study metrics will be summarized using simple descriptive statistics such as the mean, standard deviation, range, etc. Ninety-five percent confidence intervals will be computed when appropriate. A variety of graphical techniques will also be used to display data.

Light Dosimetry

In all participating sites, the light dosimetry system, described in Section 32.2, will be used to measure light dose during the entire treatment at several key locations within the treated area. The light dosimetry system will be stored and maintained in [name] laboratory at Roswell Park. The system will be provided to the site before the procedure and returned to Roswell Park, after the procedure. [name] or one of his research team members will operate the system during the I-PDT procedure.

During I-PDT, each detector will be marked (with a number) and the data from each location will be saved with information on the location and time of measurement. The primary measurable outputs will be the light fluence (J/cm²) and fluence rate (mW/cm²) at each location.

20.0 Provisions to Monitor the Data to Ensure the Safety of Subjects

All Roswell Park studies will be reviewed at the scheduled Early Phase Clinical Trial Committee meetings.

The Roswell Park Data and Safety Monitoring Committee (DSMC) will assess the progress of the study, the safety data, and critical efficacy endpoints. The DSMC will review the study and will make recommendations that include but not limited to; (a) continuation of the study, (b) modifications to the design, (c) suspension of, or (d) or termination of the study.

21.0 Vulnerable Populations

Not applicable.

22.0 Community-Based Participatory Research

Not applicable.

23.0 Sharing of Results with Subjects

Individual response data is shared with the participant as a part of their clinical care. 13MAR2023; SRC 18SEP2023; IRB 15NOV2023

24.0 Setting

Participants will receive porfimer sodium as an outpatient in the Head and Neck Clinic and PDT will occur at inpatient surgery at Roswell Park and participating sites.

25.0 Provisions to Protect the Privacy Interests of Subjects

Any data, specimens, forms, reports, video recordings, and other records that leave the site will be identified only by a participant identification number (Participant ID, PID) to maintain confidentiality. All records will be kept in a limited access environment. All computer entry and networking programs will be done using PIDs only. Information will not be released without written authorization of the participant.

26.0 Resources Available

Not Applicable.

27.0 Prior Approvals

Not Applicable.

28.0 Compensation for Research-Related Injury

For Roswell Patients only, if the subject believes they have been injured as a direct result of their participation in this research study, they will be advised to notify the Roswell Park Patient Advocate at [contact] or the Study Doctor at [contact].

Medical diagnosis and treatment for the injury will be offered, and a determination will be made regarding appropriate billing for the diagnosis and treatment of the injury. A financial counselor [contact]) will be able to provide an explanation of coverage and to answer questions the subject may have regarding study related billing.

The subject is not prevented from seeking to collect compensation for injury related to malpractice, fault, or blame on the part of those involved in the research.

29.0 Economic Burden to Subjects

The participants will not be subject to any economic burden.

30.0 Consent Process

This study will not be initiated until the protocol and informed consent document(s) have been reviewed and approved by a properly constituted Institutional Review Board (IRB) or Independent Ethics Committee (IEC). Each participant (or legal guardian) shall read, understand, and sign an instrument of informed consent prior to performance of any study-specific procedure. It is the responsibility of the investigator to ensure that the participant is made aware of the investigational nature of the treatment and that informed consent is given.

The Investigator is responsible for the retention of the participant log and participant records; although personal information may be reviewed by authorized persons, that information will be treated as strictly confidential and will not be made publicly available. The investigator is also responsible for obtaining participant authorization to access medical records and other applicable study specific information according to Health Insurance Portability and Accountability Act regulations (where applicable).

This study will be conducted in compliance with all applicable laws and regulations of the state and/or country and institution where the participant is treated. The clinical trial should be conducted in accordance with the ethical principles embodied in the Belmont Report: Ethical Principles and Guidelines for the Protection of Human Subjects of Research, consistent with good clinical practice and the applicable regulatory requirements and according to the guidelines in this protocol, including attached appendices.

31.0 Process to Document Consent in Writing

The Investigator (or IRB specified designee) is responsible for obtaining written consent from each participant in accordance with GCP guidelines using the approved informed consent form, before any study specific procedures (including screening procedures) are performed. The informed consent form acknowledges all information that must be given to the participant according to applicable GCP guidelines, including the purpose and nature of the study, the expected efficacy and possible side effects of the treatment(s), and specifying that refusal to participate will not influence further options for therapy. Any additional information that is applicable to the study must also be included. Additional national or institutionally mandated requirements for informed consent must also be adhered to. The participant should also be made aware that by signing the consent form, processing of sensitive clinical trial data and transfer to other countries for further processing is allowed.

The Investigator shall provide a copy of the signed consent form to the participant and the signed original shall be maintained in the Investigator File. A copy of the signed consent form must be filed in the participant file. At any stage, the participant may withdraw from the study and such a decision will not affect any further treatment options.

32.0 Drugs or Devices

32.1 Porfimer Sodium

The porfimer sodium will be provided, at no cost, to the patients or their insurance.

32.1.1 ACTIVE SUBSTANCE AND SOURCE

Porfimer sodium for injection is supplied as a freeze-dried cake or powder as follows: NDC 76128-155-75, 75 mg vial.

32.1.2 DRUG SHIPMENT

Porfimer sodium (Photofrin®) will be provided and shipped by Pinnacle Biologics Inc. to all participating sites. The receiving site will document the date of receipt and condition of the shipment. Drug shipment records will be retained by the investigational pharmacist or designee.

Roswell Park will provide the participating sites with instructions whom to contact and how to order the Photofrin® vials from Pinnacle Biologics Inc. The company will provide few vials when the study is approved and prior to open for enrollment at each site. More vials will be provided few days before each participant will be scheduled for treatment. The vials will be labeled and can be used for this study, only.

32.1.3 PREPARATION

Porfimer Sodium will be prepared for injection following the manufacturer instructions: "Reconstitute each vial of porfimer sodium with 31.8 mL of either 5% Dextrose Injection (USP) or 0.9% Sodium Chloride Injection (USP), resulting in a final concentration of 2.5 mg/mL: Shake well until dissolved. Do not mix porfimer sodium with other drugs in the same solution.

Porfimer sodium reconstituted with 5% Dextrose Injection (USP) or with 0.9% Sodium Chloride Injection (USP), has a pH in the range of 7 to 8. Porfimer sodium has been formulated with an overage to deliver the 75 mg labeled quantity. The reconstituted product should be protected from bright light and used immediately. Reconstituted porfimer sodium is an opaque solution, in which detection of particulate matter by visual inspection is extremely difficult. Reconstituted porfimer sodium, however, like all parenteral drug products, should be inspected visually for particulate matter and discoloration prior to administration whenever solution and container permit area from light.

32.1.4 STORAGE AND STABILITY

Porfimer sodium freeze-dried cake or powder will be stored at Controlled Room Temperature 20–25°C (68–77°F).

The Investigator or designate will be responsible for ensuring that the investigational product is securely maintained in a locked, limited-access facility, as specified by the Sponsor and in accordance with the applicable regulatory requirements.

Drug storage temperature will be maintained and recorded, as applicable.

32.1.5 HANDLING AND DISPOSAL

Under no circumstances will the Investigator supply porfimer sodium to a third party or allow it to be used in a manner other than as directed by this protocol.

32.2 Light Dosimetry System

All participating sites will have a light dosimetry system that will be used to measure the light dose [fluence rate (mW/cm²) and fluence (J/cm²)]. The dosimetry system (shown in Figure 4) has been developed at [name] laboratory at Roswell Park. This system has been used to treat patients with head a neck cancer in a compassionate care settings (36), and in ongoing studies to guide intraoperative PDT in the treatment of treat patient with lung cancer. (48) The console of this light dosimetry system is shown in **Figure 4** below. The data is recorded and stored on a password secured personal computer.

[figure not shown]

Figure 4Dosimetry System screen layout

The light dosimetry system that will be used in this study: The screen layout of the dosimetry system. The light fluence rate (mW/cm²) and fluence (J/cm²) are continuously updated during therapy and presented on a LCD screen, so the treating physician can monitor the light delivery in real-time. In this example the integration period (pointed with a red arrow) or acquisition time is 20 milliseconds (ms) to obtain high signal to noise ratio reading as shown on the right, for 630±3 nm laser light.

32.3 Laser Systems

These laser systems will be shipped before the procedure and send back after each procedure. The laser will be shipped at least one day prior to I-PDT, to allow the laser safety officer to examine the laser/s (at each participating site). The laser systems will not stay in any site, they will be shipped back and forth as described above. All participating sites will use the following or comparable laser systems:

- 1. An experimental medical PDT diode laser (ML7710-630-6W, Modulight Inc. Tampere, Finland). This system emits light with a wavelength of 630 ± 3 nm up to 6 W. It includes SMA-905 connector, fiber sensor, integrated dose calibration unit (for 10-70 mm diffuser fibers), power control, dose calibration, and a foot pedal switch. It is used under IND in another study (I 256814).
- 2. The Modulight laser (ML7710-630, medical laser system, 630 ± 3 nm, 2×2.5 W (400 μ m NA=0.22) individually controls laser fiber outputs with a SMA-905 connector and fiber sensors. It includes SMA-905 connector, fiber sensor, integrated dose calibration unit (for 10-70 mm diffuser fibers), power control, dose calibration, and a foot pedal switch.

The Modulight lasers have CE 0537, 93/42 EEC and ISO 13485 certifications to design and manufacture medical laser systems for PDT. The Modulight's ML7710-PDT platform has been specifically designed for illumination in PDT treatment processes, to meet the requirements in dose calibration, power stability and wavelength tolerance. The ML7710-630 version designed specifically for porfimer sodium. It has CB certification and design documentation for CE/FDA. These lasers, owned by Roswell Park, can reduce the treatment time significantly.

3. One or more DIOMED 630 PDT Laser. This laser system emits 630 ± 3 nm up to 2 Watts. The FDA approved the use of this laser for PDT with porfimer sodium. Pinnacle Biologics Inc.

13MAR2023; SRC 18SEP2023; IRB 15NOV2023

Roswell Park Protocol No.: I 67918

provides this laser system at no cost to physicians that administer PDT with Photofrin®. This service is offered for all customers including Roswell Park. The laser is shipped 1-2 days prior to the procedure. The laser safety officer inspects it prior to treatment. The laser is sent back (to Pinnacle Biologics, Inc.) after treatment. This arrangement has been worked well for the past few years.

32.4 Cylindrical Light Diffuser and Dosimetry fibers

The I-PDT will be accomplished by delivering diffuse red light with fiber with cylindrical light diffuser end that will be connected to one of the lasers systems described above (section 32.3). A general description of these fibers can be found in [name] et al. 2017.(47) In the study described herein, we will use fiber with cylindrical light diffuser end that can have 10, 20, 30, 40 or 50 mm length diffuser end (RD10-RD50, Medlight SA, Ecublens, Switzerland) and/or clinically approved cylindrical diffuser fibers (OPTIGUIDE® DCYL700 series 1, 1.5, 2.0, 2.5 and 5.0 cm, Pinnacle Biologics Inc. Bannockburn, IL).

For light dosimetry, we will use detection fibers with an isotropic probe end (IP, Medlight SA, Ecublens, Switzerland). We use these fibers in another clinical study that utilize PDT for the treatment of lung cancer.(48)

Medlight is ISO 13485 and ISO 9001 certified manufacturer. All their devices are CE marked, and are designed, marketed and used for PDT in the EU, and in many clinical studies. The USA FDA has successfully inspected Medlight on April 10-11, 2000.

34.0 Appendices/ Supplements

Roswell Park Protocol No.: I 67918

Appendix A ECOG Performance Status Scores

Description	Status
Fully active, able to carry on all pre-disease performance without restriction.	0
Restricted in physically strenuous activity but ambulatory and able to carry out work of a light or sedentary nature, e.g., light housework, office work.	1
Ambulatory and capable of all self-care but unable to carry out any work activities.	2
Capable of only limited self-care, confined to bed or chair more than 50% of waking hours.	3
Completely disabled. Cannot carry on any self-care. Totally confined to bed or chair.	4
Dead	5

Appendix B Inclusion Criteria Checklist

INVESTIGATOR STUDY ELIGIBILITY VERIFICATION FORM: INCLUSION CRITERIA

Partic	ipant	Name	:							
Medical Record No.: Title: A Phase 1 Trial: Porfimer Sodium Mediated Interstitial Photodynamic for the Treatment of Patients with Locally Advanced or Recurrent Head and Neck Cancer.										
INCLUSION CRITERIA										
Yes	No	N/A	N/A All answers must be "Yes" or "N/A" for participant enrollment. D							
			1.	Male or female patients age ≥ 18 years of age.						
			2.	Subjects must have an Eastern Cooperative Oncology Group (ECOG) performance status score of $0-2$. Refer to Appendix A.						
			3.	Patients with locally advanced or recurrent head and neck cancer who failed to respond to standard therapy and are not amenable to standard curative treatment						
			4.	Tumor accessible for unrestricted illumination for interstitial photodynamic Therapy (I-PDT) (accessibility as determined by the physician).						
			5.	Life expectancy of at least 6 months, in the judgment of the physician.						
			6.	Subjects of child-bearing potential must agree to use adequate contraceptive methods (e.g., hormonal or barrier method of birth control; abstinence) prior to study entry and for the duration of study participation. Should a woman become pregnant or suspect she is pregnant while she or her partner is participating in this study, she should inform her treating physician immediately.						
			7.	Subject must understand the investigational nature of this study and sign an Institutional Review Board approved written informed consent form prior to receiving any study related procedure.						
Invest	igator	Signa	atur	e: Date:						
Printe	d Nan	ne of I	[nve	stigator:						

Appendix C Exclusion Criteria Checklist

INVESTIGATOR STUDY ELIGIBILITY VERIFICATION FORM: EXCLUSION CRITERIA

Partic Medic	-								
			rial: Porfimer Sodium Mediated Interstitial Photodynamic for the T	reatment					
of Pati	ients w	ith Lo	cally Advanced or Recurrent Head and Neck Cancer.						
EXCLUSION CRITERIA									
Yes	No	N/A	All answers must be "No" or "N/A" for participant enrollment.						
			1. High dose curative radiotherapy within 30 days in the area to be treated.						
			2. Tumor invading a major blood vessel.						
			3. Tumor is not measurable on a CT or MRI scan according to RECIST v1.1.						
			4. Location and extension of the tumor precludes a potentially effective I-PDT.						
			5. Patients with known brain metastases should be excluded from this clinical trial because of their poor prognosis and because they often develop progressive neurologic dysfunction that would confound the evaluation of neurologic and other adverse events.						
			6. Patients with porphyria, or with known hypersensitivity to porphyrins or porphyrin-like compounds.						
			7. Platelet count < 75,000.						
			8. Patients with impaired renal and/or hepatic function (total serum bilirubin > 2 mg/dL, serum creatinine > 2 mg/dL, alkaline phosphatase (hepatic), SGOT or SGPT > 3 times the upper normal limit.						
			9. Patients with moderately to severely impaired creatinine clearance (CrCl <44) will be excluded.						
			10. Uncontrolled intercurrent illness including, but not limited to, ongoing or active infection, symptomatic congestive heart failure, unstable angina pectoris, cardiac arrhythmia, or psychiatric illness/social situations that would limit compliance with study requirements.						
			11. Pregnant or nursing female subjects.						
			12. Unwilling or unable to follow protocol requirements.						
			13. Any condition which in the Investigator's opinion deems the subject an unsuitable candidate to receive porfimer sodium.						
			all entry criteria:						
Invest	igator	Signa	nture: Date:						
Printe	ed Nan	ne of I	Investigator:						

Appendix D Schedule of Procedures and Observations if Only I-PDT Course is Necessary

Evaluation	Baseline ¹	Pre- Operative	Day of Treatment	Day 1 Post Treatment	1-week Post- treatment	Optional I-PDT Course 2 Within 2-3 Weeks of Day 0 ¹⁷	Clinic Visit ^{2,2a}	30- Day Post I- PDT ¹⁴	Optional I-PDT Treatment additional 2 or 3 At least 6 Weeks after last I-PDT Session ¹⁸	Follow- Up
Informed Consent	X									
Medical History	X								X	
Physical Exam/ Vital signs & pain assessment using a verbal score 0-10 ³	X				X		X	X	X	X
Hematology ⁴ and Chemistry ⁵	X				X		X	X	X	
Research Blood Draws ⁶			X		X		X	X	X	
Pregnancy Test (Urine)	X								X	
ECOG Performance Status	X		X		X		X	X	X	X
UW-QoLQ v. 4 ¹⁵	X				X		X	X	X	X
Standard Imaging of the head and neck with CT or MRI, for RECIST v11.1	X ⁷								X	X8
Treatment planning	X								X	
Porfimer Sodium administration and Vital Signs		X ⁹							X	
Intraoperative Ultrasound			X						X	
If possible, intraoperative CT or other clinically approved radiological imaging			X^{10}			X ¹⁰			X^{10}	
Interstitial PDT (I-PDT) 16			X^{11}			X ¹¹			X ¹¹	
Concomitant Medications	X ¹²		X							
Adverse Events ¹³			X		X		X	X		

Notes:

- * The I-PDT procedure is termed a "course".
 - 1. Performed within 8 weeks prior to porfimer sodium.
 - Performed at Day 1 of SOC therapy.
 If later 2nd and 3rd I-PDT courses are deemed necessary per the physician (see Section 10.4), please refer to Appendix D 1 for treatment, procedure, and test scheduling.
 - 3. Temperature, heart rate, respiratory rate, blood pressure, body weight and, height, Height collected at baseline only. Refer to Section 11.2.
 - 4. Hematology (i.e., CBC (with auto differential), ANC, and platelets). Refer to Section 11.2.
 - 5. Chemistry (i.e., AST, ALT, total bilirubin, alkaline phosphatase, creatinine, potassium, glucose, and calcium). Refer to Section 11.2.
 - 6. This is optional. Refer to immune markers Section 11.8 (1, 10 mL green-top tube).
 - 7. Standard tumor staging performed within 4 weeks, and at least 14 business days prior to I-PDT. If possible, the imaging will include temporary fiducial markers that will be affixed to skin. Refer to Section 11.2.
 - 8. CT scans at 10 to 12 weeks post SOC therapy and as clinically indicated following the NCNN 2018 guidelines.
 - 9. Infusion will occur 48 hours ± 8 h prior to illumination. Vitals are to be taken immediately after injection and after 15 minutes.
 - 10. If possible, intraoperative CT (such as O arm) or another radiological imaging (e.g. C-arm) will be used to image the catheters in the tumor.
 - 11. Refer to Section 10.2.1.
 - 12. Medications ongoing within 1 week prior to porfimer sodium injection.
 - 13. AE reporting period will be for 30 days \pm 2 days post first SOC treatment.
 - 14. First SOC treatment day of I-PDT day if no therapeutic SOC treatment is administered.
 - 15. Refer to Section 11.6f patient doesn't come in or quality of life is missed, may be done via telephone.
 - 16. In the event that the tumor size is such that treating the entire tumor could cause a health risk to the patient, the current I-PDT course will be broken up into session/s. We will illuminate one part of the tumor on the day of I-PDT and another part/s of the tumor in additional I-PDT session/s within 14 days after the initial I-PDT session, at the discretion of the treating physician. If

- an I-PDT course is broken up into I-PDT sessions, the I-PDT dosage for each session will remain the same as though sessions were not broken up as dosing is dependent on number of fibers received per session. The patient will not need to receive additional doses of porfimer sodium if having additional I-PDT sessions within 14 days after the previous I-PDT session as porfimer sodium is expected to be in the tumor for at least 30 days.
- 17. Another (one or two, total of three) laser light treatment(s) only (no additional drug) within 2-3 weeks of the initial administration of Photofrin.
- 18. Patient may receive a second complete I-PDT treatment that will include drug and light administration. It will be at the discretion of the treating physician to administer this additional treatment. Another CT (charged to the study if it is not SoC) will be done, and all tests will be conducted before and after additional treatment, according to the same schedule parameters as the initial treatment.

Appendix D 1 Schedule of Procedures and Observations (Only for Dose Escalation later I-PDT Sessions if Deemed Necessary by Physician)**

Evaluation	Repeat of Initial Tests and Procedures ^A	Pre- Operative	Day of Treatment	1-week Post- treatment	Clinic Visit	Post- Treatment	Follow- Up
Physical Exam/ Vital signs ^B & pain assessment using a verbal score 0-10	X			X	X	X	X
Hematology ^C and Chemistry ^D	X			X	X	X	
Research Blood Draws ^E			X	X	X	X	X
Pregnancy Test (Urine)	X						
ECOG Performance Status	X		X	X	X	X	X
UW-QoLQ v. 4 ^p	X			X	X	X	X
Fresh Tissue Tumor Biopsy ^F	X			X			
Standard Imaging of the head and neck with CT or MRI ^G	XH						XI
Treatment planning	X						
Porfimer Sodium administration and Vital Signs		X^{J}					
Intraoperative Ultrasound ^Q			X				
If possible, intraoperative CT or other clinically approved radiological imaging			X ^K				
Interstitial PDT (I-PDT)			$X^{L, Li}$				
Concomitant Medications	X ^M		X				
Standard of care (SoC) chemotherapy, targeted therapy or potentially immunotherapy as first line palliative care treatment options					X ^N		
Adverse Events ^O	X ^{Oi}		X	X	X	X	

Notes:

^{*} The I-PDT procedure is termed a "course". As per later Section 10.4, study participants may have up to 3 I-PDT courses per physician's discretion, at least 30 days from the previous illumination procedure.

- ** NOTE: 2nd and 3rd I-PDT courses are per the physician's discretion as per Section 10.4, 2nd and 3rd I-PDT courses are not required for all study participants. If it is decided participants should receive all 3 I-PDT courses, items from "Repeat of Initial Tests and Procedures" until the completion of I-week Post treatment" are completed twice before the Clinic Visit and start of Standard of Care chemotherapy.
 - A. Performed within 4 weeks prior to 2nd and 3rd I-PDT courses. Since there may be up to three I-PDT courses, at least 30 days apart (see Section 10.4) per the physician's discretion, the initial procedures, exams, or tests may be completed up to two more times based on the individual participant's study treatment regimen. Research blood draws, standard imaging of head and neck with CT or MRI, and treatment planning for later I-PDT courses are per physician's discretion.
 - B. Temperature, heart rate, respiratory rate, blood pressure, and body weight. Refer to Section 11.2.
 - C. Hematology (i.e., CBC (with auto differential), ANC, and platelets). Refer to Section 11.2.
 - D. Chemistry (i.e., AST, ALT, total bilirubin, alkaline phosphatase, creatinine, potassium, glucose, and calcium). Refer to Section 11.2.
 - E. This is optional. Research blood draws for any 2nd and 3rd I-PDT courses (all timepoints) are per the physician's discretion. Refer to immune markers Section 11.8 (1 green top tube).
 - F. If required per physician's discretion, standard tumor staging performed within 4 weeks, and at least 14 business days prior to following I-PDT. If possible, the imaging will include temporary fiducial markers that will be affixed to skin. Refer to Section 11.2.
 - G. CT scans at 10 to 12 weeks post I-PDT and as clinically indicated following the NCNN 2018 guidelines.
 - H. If tumor results determine porfimer sodium infusion is needed for later 2nd and 3rd I-PDT sessions, infusion will occur 48 hours ±8 h prior to illumination. Vitals are to be taken immediately after injection and after 15 minutes.
 - I. If possible, intraoperative CT (such as O arm) or another radiological imaging (e.g. C-arm) will be used to image the catheters in the tumor.
 - J. Refer to Section 10.2.1.
 - K. Medications ongoing within 1 week prior to illumination.
 - L. Refer to Section 10.2.1.
 - Li. The later 2nd and 3rd I-PDT study treatments total as per the physician's discretion are at least 30 days apart from each other (see Section 10.4). For additional I-PDT treatments that are 30 days from the previous that require an additional dosage of porfimer sodium the porfimer sodium (2mg/kg) is administered 48 hours prior to illumination.
 - M. AE reporting period will be for 30 days \pm 2 days post first SOC treatment.
 - Oi. Since there may be up to three I-PDT courses, at least 30 days apart (see Section 10.4), per the physician's discretion, adverse events review of previous study treatments are reviewed prior of the next additional I-PDT.
 - N. In Phase 1, patients are off treatment/on follow up as clinically indicated 30 days after the last I-PDT.
 - O. Refer to Section 11.6 if patient doesn't come in or quality of life is missed, may be done via telephone.

- P. In the event that the tumor size is such that treating the entire tumor could cause a health risk to the patient, the current I-PDT course will be broken up into session/s. We will illuminate one part of the tumor on the day of I-PDT and another part/s of the tumor in additional I-PDT session/s within 14 days after the initial I-PDT session, at the discretion of the treating physician. If an I-PDT course is broken up into I-PDT sessions, the I-PDT dosage for each session will remain the same as though sessions were not broken up as dosing is dependent on number of fibers received per session. The patient will not need to receive additional doses of porfimer sodium if having additional I-PDT sessions within 14 days after the previous I-PDT session as porfimer sodium is expected to be in the tumor for at least 30 days.
- Q. The intraoperative ultrasound is done for 2nd and 3rd I-PDT courses, as per physician's discretion.

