10.3 Definition of Dose-Limiting Toxicity

Dose Limiting Toxicities will include:

Any adverse events (AEs) that are \geq grade 4 that are possibly, probably, or definitely related to the I-PDT, by recording the occurrence of AE during the first 30 days post final I-PDT treatment using the revised the National Cancer Institute (NCI) Common Terminology Criteria for Adverse Events version 5.0 (CTCAE v5.0). Dose Limiting Toxicities will be evaluated for 30 days post final I-PDT day.

If participants experience DLTs, further I-PDT sessions will be held until DLT resolution as well as after porfimer sodium clearance.

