11.5 Evaluations Performed at 1st Post-Operative Clinic Visit

This visit will be scheduled 1 to 4 weeks post I-PDT and will include:

- Physical examination, including vital signs (i.e., temperature, heart rate, respiratory rate, blood pressure, body weight, and pain assessment using a verbal score of 0-10)
- Hematology (i.e., CBC (with auto differential), ANC, and platelets)
- Chemistry (i.e., AST, ALT, total bilirubin, alkaline phosphatase, creatinine, potassium, glucose, and calcium)
- ECOG Performance Status
- Adverse events
- UW QoLQ v4
- Research blood draws (Optional) #

Performed as per PI discretion if later I-PDT courses are deemed necessary as per Section 10.4.

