13.0 Risks to Subjects

This is a Greater Than Minimal Risk study according to IRB criteria. Phototoxicity is the most likely potential risk associated with the systemic administration of the porfimer sodium. Proper shielding from the procedure room lights will be maintained and the pulse oximetry sensor will be rotated every 15 minutes, to minimize this risk. The subjects will be provided with written instructions on how to protect themselves from excessive light exposure.

The site-specific toxicity associated with this therapy includes:

- a. **Injection site reaction:** Very common effects include pain at the injection site (12%) which is transient and can be minimized by slowing the injection rate. Common effects include injection site reaction (3%) and burning sensation (3%).
- b. **Tumor/local tissue reaction:** Very common effects include pain (15%), hemorrhage (15%) and scaring (12%). Common effects include edema (8%), localized infection (8%), fever (8%), and skin necrosis (2%).
- c. **Phototoxicity:** Common effects include sunburn (3%), blisters (5%), erythema (5%), hyper-pigmentation (3%), and cutaneous photosensitivity (3%).
- d. **Other systemic events:** Constipation (11%), vomiting (9%), anemia (8%), nausea (6%) and giddiness (2%).
- e. Collection of blood: Potential rare risks include local bleeding, inflammation and infection at the collection site (<1% of patients).

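### Appendix D 1 schedules a tumor biopsy before and one week after each repeat I-PDT course, but its footnote, Sections 11 and 13 and Appendix D do not support it

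*Combined protocol and SAP*

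**What the plan says.** Appendix D 1 applies to "Only for Dose Escalation later I-PDT Sessions if Deemed Necessary by Physician". Its table contains a row for "Fresh Tissue Tumor Biopsy", ticked in the column for tests repeated before a course and in the one-week column. Note A times the first of these columns: "Performed within 4 weeks prior to 2nd and 3rd I-PDT courses". It adds that these items "may be completed up to two more times based on the individual participant's study treatment regimen". Note A leaves research blood, imaging and planning for later courses to the physician's discretion; it does not name the biopsy.

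The row carries the letter F. Note F reads "If required per physician's discretion, standard tumor staging performed within 4 weeks, and at least 14 business days prior to following I-PDT" and goes on to skin fiducial markers, so it is about imaging.

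Section 11.5 covers the clinic visit in the same period ("This visit will be scheduled 1 to 4 weeks post I-PDT and will include") and lists no biopsy. Section 10.3 defines a DLT as a grade 4 or higher event that is "possibly, probably, or definitely related to the I-PDT", assessed for 30 days after the final I-PDT day.

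**The concern.** A schedule table is what study staff work from, and Appendix D sends them to Appendix D 1 for later courses. If the row is live, a participant having repeat courses would have treated tumor biopsied at about day 7. The protocol gives no purpose, method, optional status or listed risk for this.

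Safety is the primary endpoint, and dose decisions rest on 3 to 6 patients per level. An undescribed invasive procedure in treated tissue during the DLT window adds a competing explanation for a severe local event. Section 19.7 singles out life-threatening hemorrhage for attention, so clean attribution of bleeding matters here.

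**Working it through.** No stated figure is at issue. The check sets the passages side by side and does two small pieces of arithmetic.

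**1. Is the biopsy described anywhere?**

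- Section 11.2 marks the baseline items to be repeated before later sessions. No biopsy is among them, and none is listed at baseline, so there is no initial biopsy to repeat.
- Sections 11.4 and 11.5: no biopsy on the treatment day or at the first post-operative visit.
- Section 11.8 covers blood only; Section 11.9 covers resected tissue only.
- Section 2.6.2 compares surgically removed tumors. It makes the immune work optional and allows for additional samples where they can be obtained, but names no biopsy procedure or time point.
- Section 16.1: biopsy of suspected recurrence. Section 16.2: histological confirmation of partial response or stable disease, tied to the 10-12 week assessment. Neither is a pre-course or week-1 biopsy.
- Section 13 lists the risks of blood collection but none for biopsy.
- Appendix D has a column for additional I-PDT treatments and no biopsy row. Its note 18 puts the tests around an additional treatment on the first treatment's schedule, which contains no biopsy.

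Appendix D and Appendix D 1 therefore give different schedules for a repeat course.

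**2. Do the table letters fit the notes?** The Appendix D 1 notes largely reproduce the numbered notes of Appendix D, so the intended pairing can be recovered.

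| Table letter | Table entry | Note printed under that letter | Note that fits | Same note in Appendix D |
|---|---|---|---|---|
| F | Biopsy | Staging imaging | none | none |
| H | Imaging before the course | Porfimer infusion timing | F | 7 |
| I | Imaging at follow-up | Intraoperative imaging | G | 8 |
| J | Porfimer administration | Cross-reference to 10.2.1 | H | 9 |
| K | Intraoperative imaging | Medications | I | 10 |
| M | Concomitant medications | AE reporting period | K | 12 |
| O | Adverse events | Missed questionnaire | M | 13 |

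For H, I, J, K, M and O the table runs two letters ahead of the notes. Letters B to E still fit, so the shift begins around the biopsy row. That is what one would see if two notes had been deleted there and the row left in place. This is an inference from the lettering, not something the protocol states.

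**3. How many biopsies?** Ticks per repeat course = 2. Repeat courses = up to 2 (three courses less the first). Maximum per participant = 2 x 2 = 4.

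**4. How many fall in the DLT window?** The window runs from day 0 to day 30 after the final I-PDT day. With two repeat courses:

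- The two pre-course biopsies precede the final I-PDT day: outside.
- The week-1 biopsy after the second course also precedes it: outside.
- The week-1 biopsy after the third and final course is at about day 7, and 7 < 30: inside.

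So 1 of 4 is strictly inside the window.

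**The case against.** The strongest reply is that this is a stale table row and nobody would act on it: Appendix D has no biopsy, Section 11.7 names Appendix D as the schedule, and Appendix D 1 is reached only for discretionary repeat courses. The lettering supports that reading. It does not remove the problem, because the row and both ticks are legible and Appendix D's notes direct staff to this table for later courses.

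A second reply is that Section 2.6.2 supplies a plausible purpose and optional status through its tissue immune studies. That is a fair hint, and it is why the row cannot simply be assumed to be an error. But that section gives no biopsy or timing, and the row's own note does not point to it.

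A reader might also infer more than the documents support:

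- *That a bleed after the biopsy could not be told apart from an I-PDT effect.* Section 17.2.1 has five levels of attribution and expressly weighs other interventions. Attribution would be harder, not impossible.
- *That the 15% hemorrhage figure in Section 13 indicates how often this would produce a DLT.* That figure carries no grade, while a DLT needs grade 4 or higher.
- *That toxicity in single-course and multi-course participants becomes non-comparable.* No such comparison is planned; Section 19.6 pools across dose levels and cycles. Repeat-course participants already differ in treatment received, and the biopsies in 16.1 and 16.2 are taken regardless of the number of courses.
- *That participants are not told of the biopsy.* The consent pages are not available, so only its absence from Section 13 can be stated.
- *That the sponsor chose to add research biopsies.* The evidence points to inconsistent text rather than a design decision.

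**Conclusion.** The point holds as an internal inconsistency. One table row with two ticks has a footnote on another subject, no supporting procedure text and no listed risk, and it conflicts with Appendix D's schedule for additional treatments. Its reach is limited to participants given optional repeat courses, with at most four biopsies each, one of them strictly inside the DLT window.

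The effect on the dose decision is possible but cannot be quantified, because the documents give no biopsy bleeding rate. One grade 4 or higher event rated at least possibly related would move Table 2 from 0/3 to 1/3, or from 1/6 to 2/6. The same is true of any single event in cohorts this small, so it shows sensitivity, not likelihood. The conclusion assumes the table is followed as printed and that the window runs from the final I-PDT day, as Section 10.3 says. It should be corrected because staff could act on the row, even though it is probably a leftover.

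**What to change.** Reconcile the Appendix D 1 row with Appendix D (including note 18) and with Sections 2.6.2, 11 and 13. Which way to resolve it is for the sponsor to decide:

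- **If the row is a leftover**, remove it and realign every displaced note letter. That means H, I, J, K, M and O as well as F, and a check of the quality-of-life letter P, whose matching text is printed under note O.
- **If the biopsy is intended**, state its purpose, whether it is optional and its risk, and make both schedules and Section 11 agree. Record any bleed or infection after it with the biopsy date, and attribute it to the biopsy separately from I-PDT.

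The first route costs one table row and a set of footnote letters. No objective, endpoint or analysis in Sections 1, 8 or 19 names this tissue. Since Section 2.6.2 allows for optional tissue and Section 19.8 covers correlative data in general terms, the sponsor should confirm that no correlative work depends on it. The second route needs short additions to those sections and one attribution field on the case report form. Neither changes the sample size or the escalation rule.
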